##### 11.2.1 Disease Parameters

Measurable disease. Measurable lesions are defined as those that can be accurately measured in at least one dimension (longest diameter to be recorded) as  $\geq 10$  mm with MRI. All tumor measurements must be recorded in millimeters (or decimal fractions of centimeters).

For multifocal intracranial disease, no more than 5 target measurable lesions (each  $\geq 10$ mm in diameter in both dimensions) should be selected for measurement. Target lesions should be selected on the basis of their size (lesions with longest diameter), be representative of other lesions and lend themselves to reproducible repeated measurements.

Non-measurable disease. Unidimensionally measurable lesions, masses with margins not clearly defined, lesions with maximal diameter  $< 1$ cm.

##### 11.2.2 Methods for Evaluation of Disease

All measurements should be taken and recorded in metric notation using a ruler, calipers, or a digital measurement tool. All baseline evaluations should be performed as closely as

possible to the beginning of treatment and never more than 3 weeks before the beginning of the treatment.

The same method of assessment and the same technique should be used to characterize each identified and reported lesion at baseline and during follow-up. Imaging-based evaluation is preferred to evaluation by clinical examination unless the lesion(s) being followed cannot be imaged but are assessable by clinical exam.

### 11.3 Response Criteria

#### 11.3.1.1 Evaluation of Intracranial Lesions

Complete Response (CR): Requires all of the following:

- complete disappearance of all enhancing measurable and nonmeasurable disease sustained for at least 4 weeks
- no new lesions
- stable or decreasing corticosteroids (the steroid dose at the time of the scan evaluation should be no greater than the dose at time of baseline scan)
- stable or improved clinically

*Participants with non-measurable disease cannot have a complete response. The best possible response is stable disease.*

Partial Response (PR): All of the following criteria must be met:

- Greater than or equal to 50% decrease compared to baseline in the sum of products of perpendicular diameters of all measurable enhancing lesions sustained for at least 4 weeks. In the absence of a confirming scan 4 weeks later, this scan will be considered only stable disease.
- no progression of non-measurable disease.
- no new lesions
- stable or reduced corticosteroid dose (the steroid dose at the time of the scan evaluation should be no greater than the dose at time of baseline scan)
- stable or improved clinically

Progressive Disease (PD): At least one of the following must be true:

- $\geq 25\%$  increase in the sum of products of all measurable lesions over smallest sum observed (over baseline if no decrease) using the same techniques as baseline
- clear worsening of any nonmeasurable disease\*
- appearance of any new enhancing lesion/site
- clear clinical worsening (unless clearly unrelated to this cancer, e.g. seizures, medication side effects, complications of therapy, cerebrovascular events, infection)
- failure to return for evaluation due to death or deteriorating condition

\* Progression of non-measurable CNS lesions is defined as follows:

- a lesion initially at baseline  $\leq 5$ mm in diameter that increases to  $\geq 10$ mm in diameter, or
- a lesion initially at baseline 6-9 mm in diameter that increases by at least 5 mm in diameter.
- a lesion that is smaller than 10mm that is too complex or has poorly defined margins, that is now unequivocally progressing by more than 25%

Stable Disease (SD): All of the following criteria must be met:

- Does not qualify for CR, PR or progression
- All measurable and non-measurable sites must be assessed using the same techniques as baseline
- Stable clinically.

A summary of the response criteria is in the below:

	Complete Response	Partial Response	Stable Disease	Progressive Disease
T1-Gd+	None	$\geq 50\%$ decrease	<50% decrease- <25% increase	$\geq 25\%$ increase*
New Lesion	None	None	None	Present*
Corticosteroids	Stable or decrease	Stable or decrease	Stable or decrease	Stable or increasing
Clinical Status	Stable or improved	Stable or improved	Stable or improved	Decrease*
Requirement for Response	All	All	All	Any*
NA=not applicable #: Progression occurs when any of the criteria with * is present Increase in corticosteroids alone will not be taken into account in determining progression in the absence of persistent clinical deterioration				

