**3.1.3 Prior Treatment**

- Prior medical therapy is allowed but not required.
- Meningioma that have resulted from prior radiation therapy are allowed.
- No limit on number of prior therapies.
- No chemotherapy, other investigational agents within 14 days of study treatment.
- No other concurrent investigational agents or other meningioma-directed therapy (chemotherapy, radiation) while on study.
- For patients treated with external beam radiation, interstitial brachytherapy or radiosurgery, an interval  $\geq 24$  weeks must have elapsed from completion of XRT to registration.
- Stable dose of dexamethasone 2mg or less for at least 7 days prior to initiation of treatment.
- Recovered to CTCAE grade 1 or less toxicity from other agents with exception of alopecia and fatigue.
- No craniotomy within 21 days of registration.
- Grade I meningiomas will be allowed as long as they meet criteria for progression as defined by 3.1.1.

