### 5.6 Acceptable Concomitant Medications

All treatments that the investigator considers necessary for a subject’s welfare may be administered at the discretion of the investigator in keeping with the community standards of medical care. All concomitant medication will be recorded on the case report form (CRF) including all prescription, over-the-counter (OTC), herbal supplements, and IV medications and fluids. If changes occur during the trial period, documentation of drug dosage, frequency, route, and date may also be included on the CRF.

All concomitant medications received within 28 days before the first dose of trial treatment and 30 days after the last dose of trial treatment should be recorded. Concomitant medications administered after 30 days after the last dose of trial treatment should be recorded for SAEs and ECIs as defined in Section 7.4.

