### 5.7 Prohibited Concomitant Medication

Subjects are prohibited from receiving the following therapies during the Screening and Treatment Phase (including retreatment for post-complete response relapse) of this trial:

- Antineoplastic systemic chemotherapy or biological therapy
- Immunotherapy not specified in this protocol
- Chemotherapy not specified in this protocol
- Investigational agents other than pembrolizumab
- Radiation therapy
  - Note: Radiation therapy to a symptomatic lesion may be allowed at the investigator’s discretion. If radiation is given to a solitary lesion at the investigator's discretion, then the patient is considered to have progressive disease, but may continue on treatment if patient is clinically stable.
- Live vaccines within 30 days prior to the first dose of trial treatment and while participating in the trial. Examples of live vaccines include, but are not limited to, the following: intranasal influenza vaccines (e.g., Flu-Mist®), measles, mumps, rubella, varicella/zoster, yellow fever, rabies, BCG, and typhoid vaccine.

- Systemic glucocorticoids for any purpose other than to treat edema related to the meningioma or supportive post-operative management or to modulate symptoms from an event of clinical interest of suspected immunologic etiology. Intranasal, inhaled or topical corticosteroids (<5% of body surface area) for the treatment of mild/moderate asthma, allergies or dermatitis are permitted. The use of physiologic doses of corticosteroids may be approved after consultation with the Overall PI. Physiologic replacement of glucocorticoids as maintenance therapy for adrenal insufficiency are permitted. Standard doses of hydrocortisone for maintenance therapy are 10–20 mg/m^2/day divided 2–4 times per day. For a subject with a body surface area (BSA) of 1.73 m^2, this translates to a total dose of 34.6 mg of hydrocortisone per day. The equivalent dose of dexamethasone is 1.2 mg per day. Some subjects may additionally receive mineralocorticoid- replacement maintenance therapy with fludrocortisone. The maintenance dose of fludrocortisone for this indication is 0.05–0.1 mg/day. Antihistamines and other non-steroidal anti-allergy medications are also permitted.

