Scheduling Window (Days):	-14 to 0		± 3	± 3	± 3	± 3	± 3	± 3	± 3	At time of Discon	30 days post discon	Every 6 weeks	Every 3 months
Research Blood x	X	X		X		X		X		X			

aAll screening procedures to be performed within 14 days of start of study treatment, except scans which can be obtained within 21 days of starting study treatment, and informed consent may occur up to 28 days prior to start of study treatment

bC1D1 and Day 1 of subsequent cycles: For C1D1 screening assessments may serve as day 1 assessments if performed within 7 days before start of study treatment, except serum pregnancy (within 72 hours of drug) and except in the event that there are any indications that the participant's condition is deteriorating for which laboratory evaluations should be repeated within 48 hours prior to initiation. C1D1 labs must meet eligibility criteria. For all subsequent cycles, required assessments should be performed within 3 days of scheduled cycle day 1.

cStudy drug therapy administration windows include  $\pm 3$  days for each agent.

dEnd of Tx: End of treatment assessments to be performed within 7 days after last day drug administration or within 7 days after decision to end treatment. Assessments may continue for ongoing reportable adverse events.

e30-Day Post Drug: A contact/visit is to be performed at 30 days (+/-5 days) after the last study drug is given. This may be performed via documented phone conversation with a study nurse or clinician or a clinic visit. All participants will be followed until resolution or stabilization of any serious or reportable adverse events occurring during treatment or starting within 30 days of last study drug.

fActive Follow Up: In participants who discontinue study treatment without documented disease progression, every effort should be made to continue monitoring their disease status by radiologic imaging every 6 weeks (+/- 7 days) until (1) the start of new anti-cancer treatment, (2) documented disease progression, or (3) death whichever occurs first.

gLong Term Follow Up: participants will be followed every 3 months (+/- 1 month) via contact or medical record review until death for post-treatment therapies, reason for stopping those therapies and survival.

hInformed Consent: Informed Consent may be obtained within 28 days of start of study treatment

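### Stable disease carries a corticosteroid condition in the summary table but not in the text, and the CR/PR steroid rule can misclassify patients on permitted steroids

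*Combined protocol and SAP*

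**What the plan says.** All references are to the combined protocol and SAP.

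- **CR and PR (11.3.1.1, text list).** Both need stable or lower corticosteroids, explained as "the steroid dose at the time of the scan evaluation should be no greater than the dose at time of baseline scan". The indication for the steroid plays no part.
- **SD (11.3.1.1, text list).** SD is a residual category, "Does not qualify for CR, PR or progression", with two further items: same assessment technique and clinical stability. Steroids are not mentioned.
- **SD (11.3.1.1, summary table).** The steroid row, in the order CR, PR, SD, PD, reads "Corticosteroids Stable or decrease Stable or decrease Stable or decrease Stable or increasing". The last row requires all items for CR, PR and SD. The steroid entry under PD is not one of the starred triggers, and the footnote adds: "Increase in corticosteroids alone will not be taken into account in determining progression in the absence of persistent clinical deterioration".
- **Use of the categories (13.7).** Intracranial response is reported as the proportion with CR, PR or SD, with a 90% exact interval. Section 1.3 lists response rate as a secondary objective.
- **Permitted steroids (5.7, 5.5).** Systemic glucocorticoids are allowed for tumour edema, post-operative care and immune events. In addition, "Physiologic replacement of glucocorticoids as maintenance therapy for adrenal insufficiency are permitted". Section 5.5 foresees hormone replacement after hypophysitis.
- **Entry and baseline (3.1.3; Section 10, footnote a).** Entry requires "Stable dose of dexamethasone 2mg or less for at least 7 days prior to initiation of treatment". Screening falls within 14 days of treatment, "except scans which can be obtained within 21 days of starting study treatment".
- **Recording (5.6).** All concomitant medication goes on the CRF, but for changes during the trial "documentation of drug dosage, frequency, route, and date may also be included on the CRF".

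**The concern.** Steroid exposure is expected in this trial, both for edema and because Table 4 directs corticosteroids for most immune-related events. The classification rule should therefore give one answer when the dose rises. For SD it gives two, and under the table some patients fall into no category at all. Because SD counts towards the reported response proportion, the choice between text and table decides who is counted.

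The CR/PR rule raises a separate question. It treats hormone replacement like steroid given for the tumour, which can hide a response. It also takes its reference dose from a scan that may predate the entry steroid limit, which can admit a steroid-assisted response. The CR/PR rate will be read against a background that Section 2.1 puts at 0% in nearly all earlier studies, so single patients matter. Responder status also feeds the exploratory comparisons in 9.3.3, 9.3.5.3 and 13.8.

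**Working it through.** **1. The plan's own design figure.** Section 13.6 sets success at 10 or more of 24, null 26%, alternative 52%, one-sided exact test at 0.1. With X binomial(24, p):

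- P(X ≥ 10 | p = 0.26) = 0.0692, within 0.1. A cut-off of 9 would give 0.147.
- P(X ≥ 10 | p = 0.52) = 0.888, so the stated power of at least 88% reproduces.

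PFS6 depends on progression or death, and a steroid rise alone is neither. These figures do not change under any reading below.

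**2. SD, text against table.** Take a patient who is clinically stable, has no new lesion and has no progression of non-measurable disease.

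| Enhancing tumour | Steroid dose | Text list | Table |
|---|---|---|---|
| less than 50% decrease to less than 25% increase | not above baseline | SD | SD |
| less than 50% decrease to less than 25% increase | above baseline | SD | none: fails the SD steroid entry, no PD trigger |
| at least 50% decrease | above baseline | SD (PR barred) | none: fails the SD steroid entry and the SD size cell |

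The second row is the core conflict. The third shows that deleting the steroid entry alone would not align the table with the text, because the table also limits SD to less than a 50% decrease.

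**3. Size for the Section 13.7 proportion.** One patient is 1/24 = 4.2 points with the 24 evaluable patients of 13.3, or 1/26 = 3.8 points if all 26 are analysed. The documents give no SD or steroid-use rate, so the following counts are assumed for illustration. Suppose 14 patients are CR, PR or SD by the text and two of them have stable tumours with a raised dose:

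- text: 14/24 = 58.3% (90% exact CI 39.7% to 75.4%)
- table: 12/24 = 50.0% (31.9% to 68.1%)

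**4. Replacement and CR/PR.** Section 5.7 works its example as 20 mg/m² × 1.73 m² = 34.6 mg hydrocortisone and equates this to 1.2 mg dexamethasone, below the 2 mg allowed at entry.

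- Dose 0 at the baseline scan, replacement started later: 1.2 > 0, so CR/PR is barred at those scans.
- Already on the same replacement at the baseline scan: 1.2 = 1.2, condition met.
- On 2 mg dexamethasone at the baseline scan, later on replacement only: 1.2 < 2, condition met.

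The first two patients may have identical tumour shrinkage and identical current treatment, yet they are classified differently.

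**5. Reference dose.** The baseline scan may be taken up to day −21, and the dexamethasone limit is required from day −7. The gap is 21 − 7 = 14 days. A scan in that gap can carry a dose above 2 mg, and that dose then stays the reference for CR and PR. The rule becomes more lenient, the opposite direction to step 4.

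**6. Size for the CR/PR rate.** Again with assumed counts, one patient changes 2/24 = 8.3% (1.5% to 24.0%) to 1/24 = 4.2% (0.2% to 18.3%). Under the text reading, a clinically stable patient denied PR becomes SD, so the CR+PR+SD proportion does not move.

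**The case against.** The table is introduced as a summary, so one can argue that the text plainly governs and the conflict is a drafting slip. That is a fair reading, but the document does not state it, and the table is the form a reader is likely to use when classifying scans.

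Several stronger readings are tempting but not supported:

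- **Anyone on permitted hormone replacement is shut out of CR/PR for good.** Only glucocorticoid dose counts, only when it rises above the baseline-scan dose, and only at the scans concerned. Best response is taken from the start of treatment (11.3.1.2), so a response recorded earlier is kept.
- **Every misclassified patient shifts the reported response by 4.2 points.** A move between PR and SD leaves the Section 13.7 proportion unchanged. The 4.2 points apply to that proportion only where the table removes a patient from SD.
- **The high reference dose will commonly create false responses.** It is only a possibility. Section 11.2.2 asks for baseline evaluations as near to treatment as possible, 3.1.3 excludes craniotomy within 21 days of registration, and PR also needs a sustained decrease of at least 50% and clinical stability or improvement.
- **Steroid use is not captured.** The calendar marks medication review at screening only, but Section 5.6 and footnote k of Section 10 require medications to be recorded until 30 days after the last dose, and footnote k adds the reason. Only the recording of dose changes is left optional.

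Nor does a scan without a table category leave the patient without a best response, since other scans still count.

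**Conclusion.** The SD conflict is real. For a clinically stable patient with a stable tumour and a raised steroid dose, the text gives SD and the table gives nothing. Each such patient is worth 4.2 points of the reported CR+PR+SD proportion, assuming a denominator of 24.

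The two CR/PR gaps are narrower. Newly started or increased replacement can hide a response, and a baseline scan taken before the steroid window can admit a steroid-assisted one. They act on the CR/PR rate in opposite directions, and nothing in the documents shows that they cancel. Neither changes the CR+PR+SD proportion if the text governs.

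How often any of this would occur cannot be computed from the documents. A reader might infer that the primary result is at risk. It is not, because PFS6 and its design figures are untouched. The point is worth correcting because a stated secondary endpoint should have one definition, fixed before responses are classified in an open-label trial.

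**What to change.** 1. In 11.3.1.1, state that the text list governs. Remove the corticosteroid entry from the table's SD column, and replace the SD size cell with the residual definition, so that every clinically stable patient who is not CR, PR or PD is SD.
2. For response classification only, exclude physiologic glucocorticoid replacement, as 5.7 describes it, from the CR/PR steroid condition.
3. Reconcile the CR/PR reference dose with the entry steroid window in 3.1.3 and the scan window in Section 10. One option is to use the lower of the doses at the baseline scan and at Cycle 1 Day 1 as the classification reference.
4. In 5.6, make the recording of corticosteroid dose changes mandatory, so that the dose at each MRI is available to the central reviewers named in 11.3.4.

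None of this alters treatment, the entry limit or which steroids are permitted. The cost is minor wording and some data entry, with no added visit or procedure. Item 3 may turn a few steroid-assisted PRs into SD and so lower the CR/PR rate slightly.

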### 11.3.1.2 Evaluation of Best Overall Response

The best overall response is the best response recorded from the start of the treatment until disease progression/recurrence (taking as reference for progressive disease the smallest measurements recorded since the treatment started). The patient's best response assignment will depend on the achievement of both measurement and confirmation criteria. If a response recorded at one scheduled MRI does not persist at the next regular scheduled MRI, the response will still be recorded based on the prior scan, but will be designated as a non-sustained response. If the response is sustained, i.e. still present on the subsequent MRI at least four weeks later, it will be recorded as a sustained response, lasting until the time of tumor progression. Participants without

measurable disease may only achieve SD or PD as their best “response.”

### 11.3.2 Duration of Response

Duration of overall response: The duration of overall response is measured from the time measurement criteria are met for CR or PR (whichever is first recorded) until the first date that recurrent or progressive disease is objectively documented (taking as reference for progressive disease the smallest measurements recorded since the treatment started, or death due to any cause. Participants without events reported are censored at the last disease evaluation).

Duration of overall complete response: The duration of overall CR is measured from the time measurement criteria are first met for CR until the first date that progressive disease is objectively documented, or death due to any cause. Participants without events reported are censored at the last disease evaluation.

Duration of stable disease: Stable disease is measured from the start of the treatment until the criteria for progression are met, taking as reference the smallest measurements recorded since the treatment started, including the baseline measurements.

### 11.3.3 Study Continuation Beyond Initial Progressive Disease

Immunotherapeutic agents such as pembrolizumab may produce antitumor effects by potentiating endogenous cancer-specific immune responses which may manifest as initial worsening of enhancement and edema on MRI or CT scans (i.e. pseudo-progression). In addition, the response patterns seen with immunotherapeutics may extend beyond the typical time course of responses seen with cytotoxic agents, and can manifest a clinical response after an initial increase in tumor burden or even the appearance of new lesions. For these reasons, the immune-related response criteria (irRC) have endorsed continuation of study therapy beyond initial radiographic evidence of progression for clinically stable patients undergoing immune based therapies.

Therefore, the following adaptations will be used to assess response for patients treated on this study:

**Potential Pseudo-progression:** If radiologic imaging shows initial PD, subjects who are not experiencing significant clinical decline, may be allowed to continue study treatment for up to three months. Patients who have radiographic evidence of progression after up to three months (as defined by progression as in 11.3.1.1), or who decline significantly at anytime, will be classified as progressive with the date of disease progression back-dated to the first date that the subject met criteria for progression and such subjects will be discontinued from study therapy. Three months is the most common timeframe for pseudo-progression observed among patients with advanced melanoma or other solid tumors treated with PD-1/PD-L1 immune checkpoint blockade.

Among patients on this study with initial radiographic PD, tumor assessment should be

repeated regularly in order to confirm PD with the option of continuing treatment as described below while awaiting radiologic confirmation of progression. If repeat imaging shows a stabilization or reduction in the tumor burden compared to the initial scan demonstrating PD, treatment may be continued / resumed. If repeat imaging after up to three months confirms progressive disease, then the date of disease progression will be the first date the subject met criteria for progression and subjects will be discontinued from study therapy. Subjects who have confirmed disease progression will discontinue study medication and enter the follow up/survival phase of the study. In determining whether or not the tumor burden has increased or decreased, investigators should consider all target lesions as well as non-target lesions.

**Tumor Enhancement to Define Progression:** RANO expanded the previously utilized Macdonald criteria to include the development of “significantly” increased T2 or FLAIR abnormality in the definition of progressive disease because such changes can be a major component defining radiographic progression following therapeutic use of VEGF/VEGFR-targeting therapeutics which are known to elicit potent anti-permeability changes that limit contrast uptake. However, immune based therapies are expected to be associated with inflammatory changes that may include edema. Therefore, our study will define radiographic progressive disease by assessment of enhancing tumor burden only and will not include assessment of T2 or FLAIR changes as outlined in RANO because:

- There is no expectation that immunotherapy agents including PD-1 inhibitors will falsely diminish enhancing tumor burden as has been noted with anti-angiogenic therapies; and
- Immune based therapies are expected to induce inflammatory responses which may be associated with increased edema and T2/FLAIR changes. Such radiographic finding may inaccurately be interpreted to represent tumor progression (i.e. pseudoprogression).

**Treatment beyond evidence of radiographic PD:** In subjects who have initial evidence of radiographic PD, it is at the discretion of the treating physician whether to continue a subject on study treatment for up to three months pending confirmation of PD on follow-up imaging. This clinical judgment decision should be based on the subject’s overall clinical condition, including performance status, clinical symptoms, and laboratory data. Subjects may receive study treatment while waiting for confirmation of PD if they are not experiencing significant clinical decline and if:

- The subject is believed to demonstrate clinical benefit from the study regimen as determined by the treating physician;
- The subject is adequately tolerating study therapy.

When feasible, study therapy should not be discontinued until radiographic progression is confirmed. This allowance to continue treatment despite initial radiologic progression takes into account the observation that some subjects can have a transient tumor flare in the first few months after the start of immunotherapy, but with subsequent disease response. Subjects that are exhibiting significant neurologic decline are not required to

have repeat imaging for confirmation of progressive disease.

Participants with progressive radiographic findings are encouraged to undergo surgical intervention in order to delineate pseudo-progression due to inflammation associated with PD-1 blockade from true tumor progression. Participants with histopathologic findings of significant immune infiltrate and evolving gliosis will be allowed to continue study therapy. In contrast, those with clear evidence of progressive tumor by histopathologic evaluation will be defined as progressive and discontinued from study therapy. For such patients, the date of tumor progression will be the first date the participant met radiographic criteria for PD.

